For the target for “success” we will use the GSS questionnaire which will be administered on paper when the patient visits the doctor’s office for follow-up. In the study validating the GSS in SSc-associated SIBO, patients in whom the breath tests became negative after treatment had a significantly lower total GSS score than those with SIBO who did not become breath test

Pragmatic, multicentre, cluster, cohort randomised controlled treat-to-target trial for treatment of small intestinal bacterial overgrowth in systemic sclerosis (SSc) – A Pilot Project

negative (mean (range) 1.5 (0–9) vs. 8 (5–23), $p=0.001$)^{10,24}. None of the patients with eradication of SIBO had diarrhea. Hence, “no diarrhea plus a total GSS of < 5” will be the treatment target.

Meanwhile, those physicians randomly assigned to standard of care will also be informed of their patients who met eligibility criteria. They will not be aware of the detailed treatment protocol but will be informed of which medications are in the protocol eg antibiotics, prokinetics etc. They will be free to contact the patients at their convenience and to treat them in any way they deem suitable, preferably using these medications but at doses and frequencies according to their own wishes. As symptoms of SIBO tend to recur after short courses of treatment, and as the treatment protocol will be designed to adapt to this, we will follow each patient for one year from the time their physician was notified that they were eligible for the study. The primary outcome of the trial will be based on the patient reported outcomes regarding symptoms over the entire year.

What are the proposed primary and secondary outcome measures of the main trial?

Primary: The primary outcome is the total GSS score.

Secondary: Secondary outcomes include all GSS subscales. HRQoL will be assessed by the social scale of the UCLA GIT 2.0 and the NIH Promis29. Hospitalization for SIBO will be recorded during the 2 year study.

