Website Questionnaires: Subjects will access and fill in the GSS questionnaire which will be used both for screening for SIBO and for assessment of improvement with treatment. If the score of the GSS is ≥ 5 then the UCLA GIT and PROMIS GI questionnaires will also be triggered. (Appendix 4 – Questionnaires) They will be sent the link to the questionnaires via email from the central study coordinator. In this pilot, we will only screen subjects for 3 months total so the questionnaires will be filled in once a month for those 3 months. This will allow us to better assess the use of the website over a short period of time. Subjects will be notified immediately after consent is signed and thereafter once a month by email that they should fill in the questionnaire. A link will be provided. If the questionnaire is not filled out within 5 days an automatic repeat email will be sent out. We will repeat this every 5 days for a total of 3

Pragmatic, multicentre, cluster, cohort randomised controlled treat-to-target trial for treatment of small intestinal bacterial overgrowth in systemic sclerosis (SSc) – A Pilot Project

additional reminders. If there is no response after that the site coordinator will be informed and asked to phone the subject to determine and record the reason for the non-response and if the subject no longer wishes to be in the study they will be withdrawn.

Notification of Doctor of Eligible Case: If a score on the GSS is ≥ 5 , the computer will send an automatic notice to the office of the doctor and to the doctor him/herself telling them of this. The email notification will be repeated in 5 days to be sure that it has not been missed, and the provider will be asked to verify that it was received.

First Appointments: Upon receipt of the notice, the protocol doctors will be expected to make an appointment within the timeframe outline in the protocol. Standard care doctors, who will not know the details of this protocol, will decide on their own if and when to see the patient. Upon receipt of this notice the secretaries or clerks at the site will be asked to insert a treatment sheet (Appendix 5 – Treatment Sheet) in the doctor's chart. This sheet will be used to assess the timeliness of the first visit after notification, about the adherence of protocol doctors to protocol treatment and the types of medications and general pattern of treatment of the standard of care doctors.

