Pragmatic, multicentre, cluster, cohort randomised controlled treat-to-target trial for treatment of small intestinal bacterial overgrowth in systemic sclerosis (SSc) – A Pilot Project

study can each be addressed separately, by making changes to specific parts of the protocol, the success of each element will be as follows:

1. Determine if ethics committees perceive any major issues regarding the ultimate trial.

Success: There will be 10 sites and thus 10 ethics committee responses. Success will be **NO** substantive suggested changes to the protocol.

If Not Successful: **Any** suggestion for a change will be addressed for full trial.

2. Determine if the sites are approaching all yearly INSYNC patients with study and offering consent forms at the time of the visit.

Success: $\geq 80\%$ of yearly INSYNC patients are offered the consent.

If Not Successful: Interview the local research assistants or nurses and see if there seems to be a systemic issue that could be addressed to improve the frequency with which patients are approached.

3. Determine the signing rate of consent within 1 week of the time of the visit.

Success: $\geq 80\%$ acceptance rate by patients.

If Not Successful: Interview the local research assistants or nurses and see if there seems to be a systemic issue that could be addressed to improve the acceptance rate.

4. Determine patient adherence to web access for questionnaires.

Success: $\geq 70\%$ of patients go to website and answer first set of questionnaires. $\geq 90\%$ of those who answer do so within 10 days. For those who do answer first questionnaire, consider them as successes and study participants. For these subjects, do similar assessments for each subsequent questionnaire. Successful retention will be $\geq 80\%$ of those who answered each month will do so at following month.

If Not Successful: We will consider changes to the wording and frequency of reminders.

5. Assess our method for detecting eligible cases from web questionnaires.

Success: We expect that about 25% of cases will show SIBO positive responses (score ≥ 5 on GSS) to the questionnaires at some point over 3 months. In the study of 51 unselected patients with SSc, 22 (43.1%) patients were identified who fulfilled the breath test criteria of SIBO¹⁰. The sensitivity and specificity of GSS of digestive symptoms >5 to predict SIBO 0.909 and 0.862, respectively. In the 51 cases, 19 patients (37%) has scores > 5 .

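### Item 4's 80% retention bar pools notified cases with patients still being screened, so it can be met while response among the cases is well below 80%

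*Protocol*

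**What the plan says.** In The Pilot Project, Data Analyses, item 4 sets the success rule for adherence to the web questionnaires. It defines its population this way: "For those who do answer first questionnaire, consider them as successes and study participants". Retention is then successful if at least 80% "of those who answered each month will do so at following month". There is no split by GSS result. If the bar is missed, the response is to consider changing the wording and frequency of reminders.

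Item 5 gives the share expected to reach a GSS of 5 or more at some point in 3 months: "We expect that about 25% of cases will show SIBO positive responses". The word cases there means patients in the study. It also cites a published series: "In the 51 cases, 19 patients (37%) has scores" above 5.

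Under Website Questionnaires, the web GSS is "used both for screening for SIBO and for assessment of improvement with treatment", and in the pilot "the questionnaires will be filled in once a month for those 3 months". The overview of the full project makes the same web form the major outcome measure, and total GSS is the primary outcome. On who supplies that outcome, the overview says "we will follow each patient for one year from the time their physician was notified that they were eligible for the study".

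**The concern.** The web GSS does two jobs for two groups. For everyone, it detects cases. For patients already notified, it is the outcome measurement. Item 4 scores both with one number, and on item 5's expectation about three quarters of that number comes from patients who never become cases in the window.

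Equal response in the two groups cannot be taken for granted, because the protocol handles them differently. A GSS of 5 or more triggers further questionnaires and a notice to the doctor, and may lead to a visit and treatment.

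No other item fills the gap. Item 8d checks, by chart audit, in-office questionnaires at protocol visits. Item 9 has no counterpart for control sites, where doctors decide for themselves whether and when to see the patient. The web GSS is therefore the only GSS collection described for both arms, and no success criterion shows whether cases keep completing it. At stake is whether the pilot gives usable information on collecting the full trial's primary outcome.

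**Working it through.** **Inputs from the protocol.** Bar: 0.80, each month on the previous month's responders (item 4). Case share f: 0.25 (item 5), with 0.37 as sensitivity. The 25% and the 80% are stated without derivation, so there is nothing to reproduce there. The cited fraction does check: 19/51 = 37.3%.

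**Assumptions.** Non-case retention r is not given and is varied. The 25% is cumulative over 3 months; it is used here as if it were the case share at one monthly step. Monthly for 3 months is taken as three questionnaires and two steps.

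**Formula.** Pooled retention = f·x + (1 − f)·r, where x is case retention. The lowest x that still meets the bar is x = [0.80 − (1 − f)·r] / f.

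| Non-case retention r | Lowest passing x, f = 0.25 | Lowest passing x, f = 0.37 |
|---|---|---|
| 95% | (0.80 − 0.7125)/0.25 = 35% | (0.80 − 0.5985)/0.37 = 54% |
| 90% | (0.80 − 0.675)/0.25 = 50% | (0.80 − 0.567)/0.37 = 63% |
| 85% | (0.80 − 0.6375)/0.25 = 65% | (0.80 − 0.5355)/0.37 = 71% |

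**When would most cases be lost in one month?** Set x = 0.50 and solve for r. At f = 0.25, r = (0.80 − 0.125)/0.75 = 90%. At f = 0.37, r = (0.80 − 0.185)/0.63 = 97.6%. Non-case retention would have to exceed these values.

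**Two steps.** Suppose the 25% are all cases from the first questionnaire, with 85% a month in non-cases and 65% in cases. The first step gives 0.25·0.65 + 0.75·0.85 = 0.80. The second gives (0.25·0.65² + 0.75·0.85²)/0.80 = 0.6475/0.80 = 81%. Both pass, with 0.65² = 42% of cases still answering.

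**Lower case share.** Because the 25% is cumulative, the share already notified at an early step may be smaller, which dilutes cases further. At an assumed f = 0.15 and r = 90%, the lowest passing x is (0.80 − 0.765)/0.15 = 23%.

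**Precision of a case-only figure.** The protocol states no patient number. With 100, 200 or 400 responders assumed, there would be 25, 50 or 100 cases, and an observed 80% among them would have a 95% Wilson interval of 61–91%, 67–89% or 71–87%.

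**The case against.** The strongest reply is that this is a reporting breakdown. The pilot's statistics are descriptive, success does not rest on one global assessment, persistent non-responders are phoned and the reason recorded, and nothing stops the team tabulating retention by GSS status. Item 4 also measures what it names, adherence to web access, and missing the bar leads only to a look at reminders. This limits the consequence. It does not remove the point, because item 4 states a success rule, and that rule can be met without telling the team anything about cases.

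Three stronger readings are tempting, and the protocol does not support them.

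- A reader might infer that cases will drop out. No passage shows this; symptoms and contact with the clinic could equally raise response.
- A reader might infer that the bar would readily pass with most cases gone. In one month that needs non-case retention above 90% at a 25% share, and above 97.6% at 37%. The two-step example needs less, but it assumes that every case is flagged at the first questionnaire.
- A reader might infer that the bar also gives false alarms: 95% in cases and 70% in non-cases pool to 0.25·0.95 + 0.75·0.70 = 76% and fail. That failure is a correct signal, since screening supplies every case.

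One further objection stands in full. Web questionnaires are described only for the 3 screening months, while follow-up is 6 months in the pilot and a year in the full trial. A case-only figure from this schedule cannot settle whether outcome collection is feasible over that time.

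**Conclusion.** The concern holds as a statement about what the criterion can miss. On the protocol's own 25% and 80%, the bar can be met with case retention of 35% to 65% when non-cases stay at 95% to 85%. On the 37% share the range is 54% to 71%. The results rest on assumed non-case rates and on using a cumulative case share at a single step; a smaller share at that step makes the dilution stronger. They are not a forecast of drop-out among cases. The fault is modest and cheap to correct, in a rule meant to inform the design of the full trial.

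**What to change.** In item 4, replace the single retention bar by two, each at 80% or more and each reported with n/N:

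- (a) Notified cases: the share of all notified cases who answer each web GSS due after the one that made them a case.
- (b) Patients still in screening: month-to-month retention as now, until the patient's GSS first reaches 5.

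Read (a) as evidence on outcome collection and (b) as evidence on case detection; a failure of (b) remains a real failure. Add that (a) covers only the one or two monthly questionnaires left in the 3-month window, excludes cases first flagged at the last questionnaire, and is therefore early evidence and not proof of feasibility over the full follow-up.

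With all notified cases as the denominator, a case who stops answering stays in the count. This makes (a) stricter than the present rule: two successive steps at 80% would leave 0.80² = 64% and fail it. The sponsor should adopt that knowingly.

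The cost is a few sentences in item 4. No new data are needed, because case status and response both come from the web forms. The downside is precision, since (a) rests on about a quarter of participants.

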Pragmatic, multicentre, cluster, cohort randomised controlled treat-to-target trial for treatment of small intestinal bacterial overgrowth in systemic sclerosis (SSc) – A Pilot Project

This is an outline of a 9 month **pilot project** to determine the feasibility of a full scale 3 year pragmatic, multicentre, cluster, cohort randomised controlled treat-to-target trial for treatment of small intestinal bacterial overgrowth (SIBO) in systemic sclerosis (SSc).

Background:

SSc, or scleroderma, is a serious multi-system disorder of connective tissue disease characterized clinically by thickening and fibrosis of the skin and involvement of internal organs, most commonly the lungs, gastrointestinal tract and heart. SSc affects predominantly women in the prime of their life and is associated with increased morbidity and mortality. **SSc is a rare disease** with prevalence estimates varying from 30-443/million population^{1,2} which at the upper bound of 4.43/10,000 is less than 5/10,000 (500/million), the definition used by most funders for a rare disease.

The gastrointestinal tract (GIT) is the most commonly involved internal organ in SSc. GIT involvement is the presenting feature in 10%, occurs during disease course in up to 95%, and is responsible in 6-12% of all deaths in SSc patients³⁻⁹. Hypomotility of the bowel in SSc leads to **small intestinal bacterial overgrowth (SIBO) in 30–62% of patients**¹⁰⁻¹³. The most carefully performed study of the relationship of symptoms to the presence of SIBO found that symptoms occurring more commonly in patients with SIBO compared to other SSc patients are: abdominal pain/discomfort (86.4 vs 31%), bloating (77.3 vs 44.8%), diarrhea (50 vs 10.3%), constipation (59.1 vs 3.4%) and abdominal tenderness (54.5 vs. 6.9%)¹⁰.

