- patients with concomitant severe disease that would make it unlikely that they will survive for one year;
- patients with other illness or use of substances known to cause diarrhea;
- history of antibiotics in the 12 weeks prior to inclusion;
- history of intestinal pseudo-obstruction;
- inability to complete the symptom questionnaires;
- no functional level of written & spoken languages;
- previous *C. Difficile* infection;
- previous gastrointestinal surgery;
- prolonged QT interval;
- pregnancy or breastfeeding.

Screening for exclusions will be done at the site before the patient is consented. (Appendix 2- Exclusion Criteria Questionnaire)

As is typical of a pragmatic trial, we will keep inclusions broad and exclusions narrow.

Patients already on prokinetics will not be excluded but that prokinetic will be considered a failed drug and the treatment algorithm will proceed as such.

Consent and Patient Recruitment: Patients will be recruited at their regular yearly visit to their INSYNC physician or to any other participating physician. The study will be explained and they will be asked to sign a consent, (Appendix 3 – Consent Form), which will ask for their consent to be contacted by email. The email will contain a link to a website where they will be asked to fill in 2 forms, the UCLA GIT 2.0 and the GSS, on a monthly basis. They will be explained that their site will be using a specific treatment protocol or standard care and that the treatment protocol will employ much the same drugs that most physicians use for the problem of SIBO but in a very defined way. They will get a call or notice to see their doctor if they have evidence of SIBO based on their GSS test scores no matter what type of site they are assigned to.

Once a patient signs a consent, the global study coordinator will be informed that the patient is in the study via email. The email will include the patient's local study ID and their email address.

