Subsequent Appointments: The timing of subsequent appointments will be left to the discretion of the doctors but the protocol doctors will be expected to adhere to the protocol for follow up frequency and intervals. The treatment sheets will assess adherence. At each protocol visit the patient will fill out the GSS in the office as the doctor will use the score to determine success of treatment rather than relying simply on history. This is outlined in detail in the treatment protocol.

Recruitment and follow-up period: Patients will be recruited over a period of 3 months and followed up for 6 months. The total duration of the study will thus be 9 months. However, the protocol doctors will be asked to try to continue to adhere to the protocol. If there are no major changes in the protocol based on this pilot, all the patients enrolled in these 3 months may be rolled into the larger full study. This will be decided after the pilot data has been fully assessed.

Safety Monitoring: The treatment sheets will have fields to record any suspected side effects of treatment and the physicians will record this. A Data Monitoring and Safety Board (DSMB) will be established before the start of the pilot. We will request that a copy of all treatment sheets be faxed or emailed to the coordinating site after each visit. These will be forwarded to the DSMB members. If any member detects a serious side effect that they feel should lead to a change in protocol an immediate teleconference of the DSMB will be arranged.

Chart Audit: To determine if there is a disagreement between the treatment questionnaires and what the doctors actually did, we will perform a chart audit of a sample of charts. Permission to do this will be included in the consent forms. We will audit 30 % of charts randomly selected from each doctor. The audits will be of all relevant visits over the study period. We will ask to have the relevant pages from these charts faxed to us. We will find non-English speaking volunteers from the translation service at the central coordinating hospital to help fill out data extraction forms (Appendix 6 – Data Extraction Sheet) for the chart review of non-English speaking centers. The study coordinator will perform the audit.

Data Analyses: Each of the aims will be assessed. Statistics will be essentially descriptive. The success of the pilot will not depend on one global assessment. As individual elements of the

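### Item 5's expected 25% yield does not fit the protocol's own accuracy figures (47% at one reading), and it counts patients crossing a symptom cut, not SIBO detected

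*Protocol*

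**What the plan says.** Item 5 of the pilot's Data Analyses is meant to assess how eligible cases are found from the web questionnaires. Its success text is an expectation with no tolerance or direction: "We expect that about 25% of cases will show SIBO positive responses", counted if the GSS is 5 or more on any occasion in three months. In support it cites a study of 51 unselected SSc patients:

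- On prevalence, it reports that "22 (43.1%) patients were identified who fulfilled the breath test criteria of SIBO".
- On accuracy, it gives figures for a cut above 5: "The sensitivity and specificity of GSS of digestive symptoms >5 to predict SIBO 0.909 and 0.862, respectively".
- On the share of that sample above the same cut, it states: "In the 51 cases, 19 patients (37%) has scores > 5".

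The Background gives "small intestinal bacterial overgrowth (SIBO) in 30–62% of patients". Under Website Questionnaires the pilot screens monthly for three months, starting at consent. The Overview of the full trial has three-month intervals and makes a GSS of 5 or more the definition of an eligible case. No confirmatory test is described. Consent and Patient Recruitment tells patients they will be called "if they have evidence of SIBO based on their GSS test scores". If item 5 is not met, the stated action is to revise the full trial's sample size and power.

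**The concern.** A yield with no reference standard cannot show how many flagged patients have SIBO. Item 5 nevertheless labels them SIBO positive and sets accuracy figures for SIBO beside the yield. If the expected yield disagrees with those accuracy figures, the benchmark is wrong or the accuracy is not expected to hold in the pilot, and the protocol does not say which.

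Two things are at stake. The yield is the input to re-sizing the full trial, so a wrong or non-transferable figure passes straight into it. And describing the population as SIBO claims more than the entry rule supports. The pilot's patients may also be rolled into the full trial (Recruitment and follow-up period).

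**Working it through.** **Inputs (item 5 and Background).** Se = 0.909 and Sp = 0.862, both at a cut of >5; 22 of 51 with SIBO, hence 29 without; 19 of 51 stated as positive at >5; expected yield 0.25; prevalence range 30–62%.

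**1. Rebuild the cited study.**
- True positives: 0.909 × 22 = 20 (20/22 = 0.909).
- False positives: 29 − 25 = 4 (25/29 = 0.862).
- Positives: 20 + 4 = 24, and 24/51 = 47.1%.

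The stated 19/51 = 37% is not reproduced. Even if all 19 positives had SIBO, sensitivity would be 19/22 = 0.864. With the 4 false positives that the specificity requires, it would be 15/22 = 0.682. Both the accuracy and the 19/51 are given at >5, so the choice of cut does not explain the gap.

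**2. Expected yield.** One reading: yield = prev × Se + (1 − prev) × (1 − Sp).
- At 30%: 0.273 + 0.097 = 36.9%
- At 43.1%: 0.392 + 0.079 = 47.0%
- At 62%: 0.564 + 0.052 = 61.6%

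Counting a patient as positive on any of several readings can only add to these. At 43.1% prevalence, three readings give from 47% (errors repeat perfectly) to 63.5% (independent). The expected 25% is below all of them.

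**3. What a 25% yield implies.**
- Prevalence = (0.25 − 0.138)/(0.909 + 0.862 − 1) = 0.112/0.771 = 14.5%
- PPV = 0.909 × 0.145/0.25 = 53%

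These are ceilings, provided the quoted accuracy applies to the pilot. Write s and f for the ever-positive rates with and without SIBO, and y for the yield. Then prevalence = (y − f)/(s − f) and PPV = [(y − f)/y] × [s/(s − f)]. Both fall as s or f rises, and repeated readings can only raise s and f. Eligibility is at ≥5 while the accuracy is quoted at >5. The lower cut can only keep or reduce specificity, and keep or raise sensitivity, so it works in the same direction.

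**4. Size of the repeat-reading effect (assumed correlation; the protocol gives none).** Take three readings, an exchangeable latent-normal model and a within-person correlation of 0.9. Then f = 0.200 and s = 0.950. Implied prevalence is (0.25 − 0.200)/(0.950 − 0.200), about 7%, and PPV is about 25%.

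**5. PPV at the protocol's own prevalence, one reading.**
- 0.273/0.369 = 74% at 30%
- 0.392/0.470 = 83% at 43.1%
- 0.564/0.616 = 92% at 62%

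**The case against.** The strongest defence is that item 5 is a recruitment-yield check in a descriptive feasibility pilot. It concerns eligible cases, eligibility is defined by the GSS, and the only consequence of missing the figure is a revised sample size. The trial is pragmatic, its research question is about treating symptoms, and its primary outcome is the GSS itself. All of that stands. A reader might infer that a pass is meant to validate the GSS as a test for SIBO, but the protocol never says so.

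A reader might also infer that false positives alone could produce the 25%. The documents do not support that. At specificity 0.862 they reach at most 13.8% at one reading, even with no SIBO at all. Over three readings they reach 25% at zero prevalence only if the assumed within-person correlation is about 0.7 or less. At the stated prevalences they generally fall short, and true positives come on top, so the total would far exceed 25%.

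The pilot's exclusions (recent antibiotics, other causes of diarrhea, pseudo-obstruction) might lower the yield below that of an unselected sample. That is possible, but the protocol does not give it as the reason. If prevalence is lower, the PPV falls with it.

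Finally, persistence of a high score at the next reading shows stability, not SIBO, because a false positive that repeats would also persist. That is correct, and it limits such a measure to description.

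**Conclusion.** The point holds as an inconsistency and a poorly chosen measure. Item 5 expects 25% where its own source figures give 47% at one reading, and the 19/51 beside it cannot be squared with the quoted accuracy. Neither finding needs a correlation assumption. A pilot that behaved exactly like the cited study would overshoot the benchmark.

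If the quoted accuracy carries over, a 25% yield means a prevalence of at most 14.5% and a PPV of at most 53%. Any figure below that ceiling for repeat readings, such as 25% at correlation 0.9, rests on an assumed correlation. At the protocol's 30–62% prevalence the single-reading PPV is 74–92%, so the plan does not imply that most flagged patients lack SIBO. It does mean that calling every positive SIBO is more than the entry rule supports.

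The cumulative yield also depends on the number and spacing of readings. A monthly ever-positive share from the pilot therefore cannot be used directly in a trial that screens every three months.

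It would be tempting to shrink the full trial's assumed effect by the PPV. That presumes no benefit in GSS-positive patients without SIBO. The documents do not establish this, so it can serve only as a sensitivity range.

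**What to change.** 1. In item 5, report the positive share at each single reading. Base the expected figure and the full-trial sizing on the single-reading share. Reconcile the 25%, the 19/51 and the >5 versus ≥5 cut with the quoted sensitivity and specificity.
2. As a descriptive measure only, report the share of notified protocol-arm patients still at 5 or more on the first in-office GSS before treatment. The form is already planned (Subsequent Appointments): "At each protocol visit the patient will fill out the GSS in the office".
3. In item 5 and in Consent and Patient Recruitment, replace the SIBO-positive and evidence-of-SIBO labels with *GSS-positive, suspected SIBO*, and word the conclusion for symptom-defined patients.
4. Where dilution of the effect is considered in sizing, show it across the PPV range as a sensitivity analysis, not as a fixed multiplier.

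The cost is wording and one table from data already collected; no breath tests are needed. The downside is that the stated population and yield become less favourable.

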The cluster component reflects the fact that treatment will be randomized to sites rather than patients. The cohort component reflects the fact that patients will be recruited from ongoing longitudinal cohorts via web-based interactions to determine eligibility. This aspect is a variant of the cohort multiple randomized controlled trial but in which only one trial will be performed (as opposed to multiple trials)²³.

In brief, SSc patients in the International Systemic Sclerosis Inception Cohort (INSYNC) sites, of which all participants in this trial will belong, are seen for study purposes on a yearly basis, to complete detailed, standardized protocols. Data are entered into databases and subsequently harmonized across all INSYNC sites. Although the initial purpose of INSYNC was to pursue research on inception cases, (defined as < 2 years disease duration), all INSYNC sites collect data on prevalent cases as well. Thus, for the purposes of this study, all patients seen, regardless of disease duration, will be assessed at a yearly visit to see if they are able to, and will consent to, accessing a web based Gastrointestinal Symptom Score (GSS) questionnaire that they will fill out at home at regular 3 month intervals. These questionnaires will both determine their eligibility for the SIBO study and will be the major outcome measure. Before the study begins, individual sites, which will total about 30 around the world, will be randomly assigned to be treatment protocol or standard of care arms. Every 2 weeks the study coordinator will have access to the patient questionnaire results. As soon as an eligible case is detected, ie a score of ≥ 5 on the GSS, the site will be notified of this patient.

Protocol treatment sites will be expected to see the patient within a pre-specified window of time. The doctors at that site will apply the treatment algorithm and will make decisions about response to treatment based on the algorithm and on specific patient answers to questionnaires. The treatment protocol will only be made available to IRBs, not to any site personnel before randomization. This was derived from a survey of rheumatologists in many countries and gastroenterologists, mostly in North America, who were asked multiple questions about how they would treat and follow up patients with suspected SIBO. (Appendix 1- Survey of Experts)

The algorithm created for this data represents the best consensus of those opinions.

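### Do the conflicting figures quoted from the 51-patient study in Data Analyses item 5 call for a change to the plan?

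*Protocol*

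**What the plan says.** Item 5 of Data Analyses (the pilot project) sets out how the web-based detection of cases will be judged. The expectation is that about 25% of cases will reach a GSS of at least 5 at some point over three months. If that is not met, the full study's sample size and power will be revised.

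Three background statements about a cited study follow:

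- prevalence: "In the study of 51 unselected patients with SSc, 22 (43.1%) patients were identified who fulfilled the breath test criteria of SIBO";
- accuracy: "The sensitivity and specificity of GSS of digestive symptoms >5" "to predict SIBO 0.909 and 0.862, respectively";
- share scoring positive: "In the 51 cases, 19 patients (37%) has scores > 5".

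The trial's own cut-off appears elsewhere. In the Overview of the full study, the trigger is "a score of ≥ 5 on the GSS, the site will be notified of this patient". Under Notification of Doctor of Eligible Case it is "If a score on the GSS is ≥ 5". The treatment target uses the complement, "no diarrhea plus a total GSS of < 5". The sign for strictly above 5 appears only in the two sentences about the cited study.

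**The concern.** The accuracy and the count carry the same cut-off label and refer to the same 51 patients, so one should follow from the other. It does not, because the accuracy figures imply more positives than the count reports. The cited label (above 5) also differs from the trial's rule (at least 5).

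This is the only sensitivity and specificity pair the protocol gives for its screening questionnaire. As printed, a reader cannot tell whether the pair describes the rule the trial uses, or whether the share positive in the source was 37% or 47%. The figures also stand beside the 25% expectation, and missing that expectation leads to a revision of the full trial's sample size. If the 25% had been worked out from a wrong figure, the planning of the main trial would inherit the error.

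**Working it through.** **Inputs**, all from item 5: N = 51; with SIBO = 22; sensitivity 0.909; specificity 0.862; stated positives = 19 (37%).

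**Step 1. Reproduce the stated percentages.** 22/51 = 43.1% and 19/51 = 37.3%. Each count agrees with its own percentage, so neither looks like a misread digit.

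**Step 2. Confirm the denominators.** Without SIBO: 51 − 22 = 29. The Background section gives symptom rates by SIBO status from the same reference, and all ten are whole counts over 22 and 29:

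- with SIBO: 86.4% = 19/22, 77.3% = 17/22, 50% = 11/22, 59.1% = 13/22, 54.5% = 12/22;
- without SIBO: 31% = 9/29, 44.8% = 13/29, 10.3% = 3/29, 3.4% = 1/29, 6.9% = 2/29.

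**Step 3. Recover the counts behind the accuracy figures.**

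- Sensitivity = true positives / 22. Only 20/22 = 0.909 fits (19/22 = 0.864, 21/22 = 0.955).
- Specificity = true negatives / 29. Only 25/29 = 0.862 fits (24/29 = 0.828, 26/29 = 0.897).
- Positives = 20 + (29 − 25) = 24, and 24/51 = 47.1%.

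**Step 4. Compare.** 24 − 19 = 5 patients. Nineteen positives cannot contain 20 true positives; with 19, sensitivity could be at most 19/22 = 0.864. The mismatch is one of exact counts, so sampling error has no bearing on it.

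**Step 5. Try other readings.**

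- Swapping sensitivity and specificity with 22 cases gives no whole-number table. Swapping them and also reversing the 22/29 split gives 25 + 2 = 27 positives.
- If some scores were missing, 0.862 would still need 25/29, and 0.909 would need 20/22 or 10/11. Positives would be 24 or 14, never 19.
- If both sentences were meant to read at least 5, the conflict stays.
- If the accuracy belongs to at least 5 and the count to above 5, the figures agree provided exactly five patients scored 5. The protocol does not say this. It does report a range starting at 5 among patients who stayed breath-test positive after treatment, so a score of 5 can occur, but those are post-treatment scores.

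**Step 6. Trace where the figures are used.**

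| Element of the plan | Uses 19, 37%, 0.909 or 0.862? |
|---|---|
| Detection and notification | No; fixed at a score of at least 5 |
| Treatment target | No; justified separately by score ranges of 0–9 and 5–23 in the validation study |
| Expected yield of about 25% | No formula links it to them; it is below both 37% and 47% |
| Revision of the full study's sample size | No; triggered by the share observed in the pilot |
| Pilot analysis | No; descriptive |

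**The case for a change.** The strongest case for acting is that the contradiction is exact, needs nothing beyond three neighbouring sentences, and survives every alternative reading except one that the text does not state. A sign lost when the PDF was read is a weak excuse, since the at-least sign is printed correctly earlier in the same item, and losing it from both sentences would not reconcile them. The accuracy pair is the protocol's only such evidence for its screening tool, it is attached to a cut-off the trial does not use, and putting it right would cost one sentence.

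The arithmetic stands in full, and the protocol is wrong as printed. Two parts of the case do not carry. Reporting a source at its own cut-off is not an error, so the difference between above 5 and at least 5 is a fault only as far as it adds to the mismatch. And nearness to the 25% expectation does not make the figures an input to it. The 25% is stated as a judgement, and both candidate shares exceed it, so choosing between them would not reverse how it compares with the source. What counts for the full trial is the proportion the pilot itself observes at the trial's own cut-off.

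**Conclusion.** The internal inconsistency is certain: five of 51 patients, 24 (47%) implied against 19 (37%) stated. It is a clerical slip in background rationale, and no change to the plan follows. The operating rule is unambiguous, nothing is calculated from the disputed figures, and the pilot will supply its own estimate of the share positive. With any of the possible corrections, the same patients would be flagged, the same notices sent and the same results reported.

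This rests on two points. First, the 25% expectation is a judgement and not a hidden calculation from the cited share; the protocol shows no derivation. Second, the documents cannot show whether the count, the accuracy or the cut-off label is wrong, because the cited study is not at hand. Anyone who later wants to use the 0.909 and 0.862 pair, for instance in planning the full trial, should look up the cut-off in the source first.
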